## **14.0 Withdrawal of Subjects**

Subjects may withdraw at any time without penalty. Reasons and partial data will be documented. Participants who withdraw due to AEs will receive appropriate medical evaluation.

## **15.0 Risks to Subjects**

Transcranial direct current stimulation (tDCS) has been shown to safe when used within standard parameters (up to 4 mA, sessions under 40–60 minutes), with no evidence of serious or irreversible adverse effects reported across tens of thousands of sessions, including in vulnerable populations such as children, the elderly, and patients with neurological conditions (Bikson et al., 2016; Grossman et al., 2019; Ko, 2021). Furthermore, this newly invented High-Capacity tDCS device was recently studied in healthy volunteers and found to be tolerated and safe up to 6 mA for 30 minutes, with minimal discomfort and no skin injury (Donnery et al., 2025). The most commonly reported side effects in tCDS research are mild and transient, including itching, tingling, headache, burning sensations, and discomfort at the site of electrode placement, with these effects occurring at similar rates in both active and sham (placebo) groups (Aparicio et al., 2016; A. Brunoni et al., 2011; Nikolin et al., 2017). There is no evidence that repeated sessions increase the risk of adverse events, nor that any specific patient group is at higher risk under standard protocols (Chhatbar et al., 2017; Russo et al., 2017). Animal studies suggest that the electrical doses used in tDCS are far below levels that could cause brain tissue damage (Bikson et al., 2016; Ko, 2021).

### **1. Transient Skin Erythema / Redness**

Local redness or mild warmth is common beneath the stimulation pads. This reaction is expected to resolve within 30–60 minutes. Participants will be advised to apply vitamin E or an aloe-based cream if erythema persists longer than 2 hours. Any Grade  $\geq 2$  skin event will be documented and reviewed prior to the next stimulation day.

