### **3.0 Intervention to be Studied**

The intervention we are studying is called high-dose transcranial direct current stimulation (tDCS). tDCS is a non-invasive form of neuromodulation that delivers a low-intensity electrical current through electrodes placed on the scalp to modulate cortical excitability. The device used in this trial is a modified version of the Soterix Medical 1x1 tDCS system, a platform with a strong safety record and use in hundreds of clinical trials worldwide. The modified “High Capacity” (HC-1x1) version in this study will be configured to deliver up to 6 mA of current with a ramp-up period extended from 60 seconds to 120 seconds to enhance comfort. In addition, the maximum voltage will be reduced approximately fivefold to improve tolerability further.

Stimulation will be delivered using self-adhesive hydrogel electrodes manufactured in the laboratory of [name], connected to the output of the modified 1x1 device. Electrodes will be positioned in a bifrontal montage, with the anode over the left frontal region and the cathode over the right frontal region. The device will be activated for 20 minutes per session, with twice-daily sessions separated by at least 30 minutes during the main protocol phase.

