**Day 1 (dose-escalation safety assessment cohort: first 3 patients enrolled):**

- 20-minute stimulation at **2 mA** → 30-minute rest period (extendable to 60 minutes if needed)
- 20-minute stimulation at **4 mA** → 30-minute rest period (extendable to 60 minutes if needed)
- 20-minute stimulation at **6 mA**

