**Day 2 (skin integrity and safety check):**

- Visual inspection of electrode sites for erythema, burns, or other skin reactions, and completion of the tDCS Adverse Event Questionnaire
- If no **serious adverse event (SAE)** requiring emergency department evaluation or hospitalization is observed, and skin integrity is deemed acceptable by clinical evaluation by on-site MD, participants will proceed to:
  - Two 20-minute stimulation sessions at **6 mA**, separated by a 30-minute-60 to 60-minute rest period for the remaining 4 days.
  - **Main Protocol (remaining 9 participants):** Progression beyond the initial safety run-in cohort will occur only after the Safety Review Committee has reviewed the adverse event data, skin integrity assessments, and tolerability questionnaire responses from the first three participants and determined that continuation at 6 mA is acceptable.
    - Same procedure as above, including consent, neuropsychological testing, pregnancy testing (if applicable), and MRI
    - Instead of starting at 2 mA, participants will start at 2 sessions/day at 6 mA (20 min each, 30-minute interval),
    - Conducted in-lab over 5 consecutive weekdays. After each session, skin and safety checks will be completed by study staff or trained personnel.

- **Post-Treatment Assessment:**

- Conducted in-person after the last stimulation session
- Virtual follow-up at 4 weeks to assess durability. Pt's will answer the same neuropsychological questions as above.

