### **2. Skin Irritation, Dermatitis, or Superficial Burns**

Prolonged or repeated sessions at higher current density may produce focal irritation, itching, or—rarely—superficial burn/necrosis. All electrode sites will be inspected before and after each session.

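### The review of a Grade ≥2 skin event is due by the next stimulation day, although sessions repeat on the same day from 30 minutes apart

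*Protocol*

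**What the plan says.** Section 15.0, item 1, requires that any Grade ≥2 "skin event will be documented and reviewed prior to the next stimulation day". Of ordinary redness under the pads, the same item says "This reaction is expected to resolve within 30–60 minutes".

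Section 3.0 describes 20-minute sessions, "with twice-daily sessions separated by at least 30 minutes during the main protocol phase". Section 10.0 gives the main phase two 6 mA sessions a day and adds "Conducted in-lab over 5 consecutive weekdays". The first three participants receive 2, 4 and 6 mA on Day 1, with 30-minute rests that may be stretched to 60. They then have two 6 mA sessions a day for the remaining four days.

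Several safeguards surround this:

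- Section 15.0, item 2: "All electrode sites will be inspected before and after each session".
- Section 10.0, main phase: "After each session, skin and safety checks will be completed by study staff or trained personnel".
- Section 10.0, run-in Day 2: if there is no serious adverse event and "skin integrity is deemed acceptable by clinical evaluation by on-site MD, participants will proceed to" the 6 mA sessions.
- Section 10.0: the Safety Review Committee must review adverse events, skin assessments and tolerability data from the first three participants before the main phase begins.
- Sections 7.0 and 13.0: clinical supervision is on site and co-investigators attend the sessions.

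**The concern.** The review deadline and the stimulation schedule run on different units. A site could follow the Grade ≥2 rule to the letter and still stimulate the same skin again, or raise the current, before the review falls due.

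The rest between two same-day sessions is when a review can still change what the participant receives. Section 15.0, item 2, itself links repeated sessions at higher current density to focal irritation and, rarely, superficial burn or necrosis. Section 2.0 says that this device and dose are untested in a clinical population. Section 5.0 excludes people with irritated, burned or broken skin at the electrode site, yet no text applies that standard between sessions on the same day. The protocol does attach an action to a finding elsewhere: Section 15.0, item 7, ties a fall of 20% or more in blood pressure or heart rate to dose reduction or discontinuation.

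**Working it through.** The protocol states no figure on this point to reproduce. The check is a count of sessions and gaps from the schedule in Sections 3.0 and 10.0, set against the review deadline.

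**1. Main phase.** Sessions: 5 days × 2 = 10. Gaps between consecutive sessions: 10 − 1 = 9. Same-day gaps: 5 (one per day). Overnight gaps: 9 − 5 = 4. The review deadline operates only in the 4 overnight gaps.

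**2. Run-in.** Sessions: 3 on Day 1 + 4 × 2 on Days 2 to 5 = 11. Gaps: 11 − 1 = 10. Same-day gaps: 2 on Day 1 + 4 on Days 2 to 5 = 6. Overnight gaps: 10 − 6 = 4. The two Day 1 gaps are the steps from 2 to 4 mA and from 4 to 6 mA.

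**3. Timing, in minutes after the end of the day's first session.**

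| Session | 30-minute rests | 60-minute rests |
|---|---|---|
| Second session of the day (4 mA step on run-in Day 1) | 30 to 50 | 60 to 80 |
| 6 mA step on run-in Day 1 | 30 + 20 + 30 = 80, to 100 | 60 + 20 + 60 = 140, to 160 |

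With a 30-minute rest, the second session falls inside the 30 to 60 minutes in which ordinary redness is expected to fade. Staff must then judge whether a reaction is transient or Grade ≥2 at a point where the text does not require the review.

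**4. Does other text supply the missing hold?**

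- The inspections before and after each session ensure that the site is seen. They name no finding that stops the next session.
- The post-session checks in the main phase may be done by study staff or trained personnel, and no physician clearance follows from them.
- The Day 2 physician check is a real go/no-go decision, but it comes after all three Day 1 steps. It does not cover the second session on Days 2 to 5.
- The Safety Review Committee decides whether the main phase may start. It does not act between two sessions of one participant.

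**5. Day 5.** No stimulation day follows, so a Grade ≥2 event in either Day 5 session has no stated review deadline.

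**6. Effect of the change.** With the review due before the next session, the same-day gaps without a due review fall from 5 to 0 in the main phase and from 6 to 0 in the run-in.

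**The case against.** The best defence is that the deadline is an outer limit and does not permit re-stimulation. An inspection before each session has little purpose unless its result can stop that session, and qualified staff are present to act on it. A next-day look also has its own use: the endpoint in Section 4.0 defines significant irritation partly by redness lasting more than 24 hours, which nobody can judge in a 30-minute rest. The two Day 1 gaps follow only 2 and 4 mA, which Section 15.0 places within standard parameters. The run-in participants' first 6 mA session closes Day 1, and the physician check precedes their second. The main phase opens only after the Safety Review Committee has accepted 6 mA.

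Most of this stands, and it is why the point is minor. It does not close the gap, because none of these safeguards says that a Grade ≥2 finding holds the next same-day session. That step is left to good practice.

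Three stronger readings are tempting, and the protocol does not support them:

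- **That skin goes unchecked between sessions.** It is inspected before and after each one.
- **That participants face a demonstrated risk of injury.** The protocol gives no Grade ≥2 rate. Section 15.0 reports no skin injury in healthy volunteers at 6 mA for 30 minutes, and Section 18.0 puts current and charge density below those of High Definition tDCS.
- **That the main-phase rest is too short for a review.** Sections 3.0 and 18.0 make 30 minutes a minimum with no upper limit.

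How Grade is defined, and how a withheld session counts in the endpoint, are separate matters that this point does not need.

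**Conclusion.** The point holds as a badly timed rule and is minor in severity. The Grade ≥2 review is tied to the day while stimulation is tied to the session. The wording therefore leaves 5 of 9 main-phase gaps and 6 of 10 run-in gaps without a due review, and Day 5 without a deadline. The counts assume that the schedule in Section 10.0 is delivered in full. They measure the reach of the wording and say nothing about how often a Grade ≥2 event will occur. The existing inspections, the Day 2 physician check and the committee review make it likely that a serious reaction would be noticed and acted on. The protocol should nevertheless require that action. No statistical figure changes.

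**What to change.** In Section 15.0, item 1, change the deadline from the day to the session. Suggested content: a Grade ≥2 reaction is recorded and reviewed before the next stimulation session, including each current step on run-in Day 1; that session goes ahead only once the on-site clinician has cleared the site; after the final session, the review takes place at the in-person post-treatment assessment.

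This is one sentence. The inspections, the clinical staff and the post-treatment assessment are already in the protocol, so no visit or post is added. Section 4.0 needs no edit for this point, and Grade need not be redefined.

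The downside is that an occasional same-day session is delayed or, rarely, missed. A delayed session that is still given costs only time. A missed one could lower the tolerated proportion slightly, because that endpoint requires all scheduled sessions to be completed. The denominator is not stated. As a range, one affected participant moves the proportion by 1/20 = 5.0 percentage points if all 20 enrolled count, or by 1/12 = 8.3 points if only the 12 expected completers count.

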### **2. Skin Irritation, Dermatitis, or Superficial Burns**

Prolonged or repeated sessions at higher current density may produce focal irritation, itching, or—rarely—superficial burn/necrosis. All electrode sites will be inspected before and after each session.

### **3. Tingling, Itching, or Pressure Sensation**

Mild paresthesia under the pads (described as tingling, itching, or pressure) is typical and generally subsides shortly after the current is offset.

### **4. Headache, Dizziness, or Facial Pain**

Low-intensity electrical stimulation of the scalp can occasionally provoke a headache or transient dizziness. These symptoms usually resolve within minutes. Participants will be seated during stimulation to minimize fall risk; fluids and rest will be offered if symptoms persist.

### **5. Mood Destabilization or Induction of Mania**

Although rare, neuromodulation studies in depression have reported emergent hypomanic or manic symptoms. Systematic reviews and meta-analyses have documented a small

number of cases—six instances of affective switching (from depression to mania or hypomania) were observed in studies of tDCS for bipolar depression, and a total of 11 cases have been reported in patients with depression across the literature, though the overall incidence is very low and a direct causal relationship is difficult to establish due to the limited number of subjects and events (Antal et al., 2017; A. R. Brunoni et al., 2017; Dondé et al., 2017; Matsumoto & Ugawa, 2016). Participants will complete brief mood screens daily; any sign of treatment-emergent mania will prompt psychiatric evaluation and possible withdrawal from the study.

#### **6. Seizure**

The delivered current ( $\leq 6$  mA) and charge density are well below established seizure thresholds; nonetheless, a new-onset seizure is considered a Serious Adverse Event (SAE). In our review of the literature, there is only one case report of a tCDS being associated with seizure, and this was in a child with epilepsy (Ekici, 2015). Emergency response equipment and ACLS-trained personnel will be immediately available; the IRB will be notified within 24 hours of any seizure.

#### **7. Cardiovascular Changes**

Transcranial direct current stimulation is not typically associated with heart-rate variability, but autonomic shifts cannot be ruled out. Vital signs will be obtained pre-session and once hourly during Days 1–7. Clinically significant hypotension/bradycardia ( $\geq 20$  % decline from baseline) will lead to dose reduction or discontinuation.

#### **8. Device Malfunction**

Unintended rapid discharge or incomplete current delivery could result from device failure. Any malfunctioning of the device will be uploaded to RedCaps. Malfunctioning devices will be removed and quarantined for engineering review.

#### **9. Unknown Risks**

HC-tDCS is a novel, higher-dose form factor; unanticipated AEs are possible. New information that could alter the risk–benefit profile will be promptly communicated to participants and the IRB.

#### **10. Loss of Confidentiality**

As with any study collecting personal data, there is a small risk of a privacy breach. Data protections (encrypted REDCap, coded identifiers, limited-access servers) are in place, and any breach would be reported per MUSC policy.

#### **11. Questionnaire-Related Distress**

Some survey items address depressive symptoms and suicidal ideation. Participants may skip any item or discontinue assessments; immediate clinical support from study psychiatrists is available.

### **16.0 Potential Benefits**

**To the Participant:** Participants may experience improvement in depressive symptoms as a result of receiving high-dose transcranial direct current stimulation (tDCS). While the primary purpose of this study is to evaluate safety, tolerability, and feasibility, tDCS has been shown in prior research to produce clinically meaningful reductions in depressive symptoms, particularly in non-treatment-resistant populations. Participants will receive repeated, structured stimulation sessions under close clinical supervision, and their mood, anxiety, and related symptoms will be regularly monitored. This may allow for earlier identification of symptom changes and facilitate appropriate clinical follow-up if needed. Although symptom improvement cannot be guaranteed,

participants may benefit from access to a novel, non-pharmacologic intervention that is not yet widely available in clinical settings.

**To Society:** If shown to be safe, tolerable, and feasible, this study could lay the groundwork for a scalable, accessible brain stimulation intervention for Major Depressive Disorder. Current neuromodulation treatments are generally limited to treatment-resistant populations and require in-clinic administration, restricting their accessibility. The findings from this study could inform larger efficacy trials and ultimately contribute to the development of a first-line, non-pharmacologic treatment option that could be deployed in primary care and outpatient psychiatry settings. Such a treatment could expand the therapeutic toolkit for depression, reduce reliance on medications with systemic side effects, and improve the quality of life for a broad range of patients.

## **17.0 Sharing of Results with Subjects**

Aggregate results will be posted on ClinicalTrials.gov and shared upon request. Clinically actionable incidental findings will be communicated individually.

## **18.0 Drugs or Devices**

The device used in this trial is a modified version of the Soterix Medical 1x1 tDCS system, a platform with a strong safety record and use in hundreds of clinical trials worldwide. The modified “High Capacity” (HC-1x1) version in this study will be configured to deliver up to 6 mA of current with a ramp-up period extended from 60 seconds to 120 seconds to enhance comfort. In addition, the maximum voltage will be reduced approximately fivefold to further improve tolerability.

Stimulation will be delivered using self-adhesive hydrogel electrodes manufactured in the laboratory of [name], connected to the output of the modified 1x1 device. Electrodes will be positioned in a bifrontal montage, with the anode over the left frontal region and the cathode over the right frontal region. The device will be activated for 20 minutes per session, with twice-daily sessions separated by at least 30 minutes during the main protocol phase.

tDCS is a non-significant risk method that has been approved in many studies by the MUSC IRB, of which [name] has been a co-author (Borckardt et al., 2012; George & Aston-Jones, 2010; Glaser et al., 2016). The intervention under investigation involves the use of a tDCS hydrogel electrode (High Capacity, HC). Compared to the typical sponge electrodes, HC electrodes are designed for superior delivery of current across the skin, which in turn reduces the sensations felt at the skin, allowing the use of higher current, for example, 6 mA. Based on tDCS safety studies and standards, while most trials use 2 mA, this is not a safety limit but rather related to skin sensations. 6 mA remains well below safety limits reported (~50 mA) (Bikson et al., 2016). In regard to electrode current density and charge density, HC-tDCS with 6 mA is less than “High Definition tDCS,” which is also well established to be safe, including trials at MUSC

(Borckardt et al., 2012). Based on the prior work in healthy subjects, we expect 6 mA HD-tDCS to be well tolerated in a clinical population of MDD.

The device used for this study is the Soterix Medical 1x1 HC-tDCS device, which is a medical-grade investigational device (ie, not approved by the FDA for treatment of any disease). The 1x1 HC-tDCS device is based on the Soterix Medical 1x1 tDCS platform, which has been used in hundreds of clinical trials under NSR, is CE marked, and broadly considered a quality standard in tES. The standard models have been modified to allow the higher current needed in the trial, along with a slower ramp and reduced voltage compliance to further enhance tolerability.

